To assess the clinical outcome over 6 months following treatment with non-surgical debridement using a Er: YAG laser device (AdvErL EVO, Morita corporation, Japan) or with the use mechanical therapy using ultrasonic device with a specially designed tip (EMS, Switzerland)

Materials and methods

Outcome variables

- The extent of gingival inflammation (bleeding on probing BOP)
- Clinical probing pocket depth values
- Clinical registration of suppuration
- Recession of the peri-implant mucosal margin at test and control sites between baseline and at study endpoint (6 months)
- The treatment times
- Changes in "bone levels" (measured from periapical radiographs (see below)
- The prevalence of implant loss

Subject screening

Exclusion criteria

- Subjects with uncontrolled diabetes mellitus (HbA1c > 6.5)
- Subjects requiring prophylactic antibiotics
- Subjects taking prednisolone
- Subjects taking medications known to have effects on gingival growth

• Subjects with a history of taking systemic antibiotics in the preceding 1 month

Inclusion criteria - Presence of peri-implant mucositis

Following a review of the medical history (see exclusion criteria) a full mouth routine periodontal examination, including analysis of available radiographs, will be performed. Subjects who consent and:

- Have a minimum of one or more peri-implant sites with probing depth ≥ 4 mm combined with bleeding and/or pus on probing using 0.2 N probing force.
- 2. No peri-implant marginal bone loss (as determined from a comparison of the bone level one year following implant reconstruction with the bone level at screening (screening radiograph)
- A limited allowed bone loss ≤ 2mm measured from the implant shoulder (as a consequence of remodeling during the healing process)

Intraoral radiographs

Intraoral standardized radiographs of the site of interest will be taken at baseline and at 6 months. Radiographs will be analysed by an independent and blinded examiner.

Treatment procedure

Baseline measurements will be performed, and the patients are randomized into treatment groups A or B. The treatment will be performed by a dentist not involved in the registrations in order to avoid bias. Following treatment, the patients will be instructed in proper homecare using a toothbrush and interproximal aids as needed.

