Allocation concealment

Assignment to test and control group will be made using pre-prepared randomization in groups A or B. Cards with group identification will be prepared and placed in numbered envelopes after randomization. This will be done by a person not involved in the treatment or diagnosis of patients. As a new patient is admitted to the study the treating clinician takes the next numbered envelope then assigning the patient to either group A or B. The code for treatment A and B will be broken once the study is completed and the data set is locked.

Clinical registrations and treatment at baseline

- Clinical photo
- Presence/absence of plaque (6 sites/implant)
- PPD (6 sites/implant)

- Recession of the buccal mucosal margin
- BOP (6 sites/implant) graded
- Presence/absence of suppuration (6 sites/implant)
- FMPS (4 sites per tooth/implant)
- FMBS (4 sites per tooth/implant)
- Prescence/absence of hyperplasia
- Radiograph of the treated site
- Oral hygiene instruction + subgingival treatment in accordance to randomization
- Patient evaluation of the treatment including a VAS scale for pain. And another for aesthetic/satisfaction. OHIP-14 for quality of life assessment in relation to oral health.

Clinical registrations - 1 month

- Clinical photo
- Presence/absence of plaque (6 sites/implant)
- PPD (6 sites/implant)
- BOP (6 sites/implant) graded
- Presence/absence of suppuration (6 sites/implant
- FMPS (4 sites per tooth/implant)
- Re-instructions in oral hygiene procedures

Clinical registrations and supportive treatment at 3 months

- Clinical photo
- Presence/absence of plaque (6 sites/implant)
- PPD (6 sites/implant)
- Recession of the buccal mucosal margin
- BOP (6 sites/implant) graded
- Presence/absence of suppuration (6 sites/implant)

- Presence/absence of hyperplasia
- FMPS (4 sites per tooth/implant)
- FMBS (4 sites per tooth/implant)
- Oral hygiene instruction + subgingival treatment in accordance to randomization
- Patient evaluation of the treatment including a VAS scale for pain.

Clinical registrations and therapy at 6 months

- Clinical photo
- Presence/absence of plaque (6 sites/implant)
- PPD (6 sites/implant)
- Recession of the buccal mucosal margin
- BOP (6 sites/implant) graded
- Presence/absence of suppuration (6 sites/implant)
- Presence/absence of hyperplasia
- FMPS (4 sites per tooth/implant)
- FMBS (4 sites per tooth/implant)
- Radiograph of the treated site.

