[figure not shown]
TREATMENT OF PERI-IMPLANT MUCOSITIS USING AN ER: YAG LASER OR AN ULTRASONIC DEVICE. A RANDOMIZED CLINICAL TRIAL.

Statistical analysis plan NCT 05772299

Statistical analysis plan in the study. "Treatment of periimplant mucositis using an Er: Yag laser or an ultrasonic device. A randomized clinical trial."

The power analysis was based on: If bleeding on probing (BOP) is reduced with $30\% \pm 10$ in the test group and with a $30\% \pm 10$ decrease in the control group, detected at alpha= 0.05 and a power of beta= 0.2. The power analysis showed a minimum of 38 individuals to reach a significant difference. It will be foreseen to incorporate 45 individuals if some of the individuals will not fulfil the study.

The IBM SPSS version 28.0 statistical software package (SPSS Inc., Armonk, NY, USA) for personal computer will be used in the statistical analyses.

Statistics will be calculated as means and standard deviation (SD). To compare inter and intra group differences independent t-test (equal variance not assumed), paired t-test and one-way ANOVA test will be used.

For categorical variables non-parametric chi-square test will be used. Statistical significance will be set with 80% and at p< 0.05.

Non visits will be recorded as missing data in the statistics.

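### The SAP names no paired test for categorical outcomes, so chi-square used for within-group change in suppuration or hyperplasia would treat paired data as independent

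*SAP*

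**What the plan says.** The SAP's paragraph on tests reads "To compare inter and intra group differences independent t-test (equal variance not assumed), paired t-test and one-way ANOVA test will be used". The sentence thus names an unpaired and a paired procedure for means. The categorical rule follows separately: "For categorical variables non-parametric chi-square test will be used". The SAP names no paired or repeated-measures method for categorical data, and the protocol names no tests at all. The threshold is given as "Statistical significance will be set with 80% and at p< 0.05", with no statement of one- or two-sided testing.

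The protocol's *Outcome variables* list includes "Clinical registration of suppuration". The visit lists have it scored as present or absent at 6 sites per implant at baseline, 1, 3 and 6 months. Hyperplasia is also binary ("Presence/absence of hyperplasia"), recorded at baseline, 3 and 6 months, but it is not in the outcome list. Neither document says when a patient, as opposed to a site, counts as positive.

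**The concern.** The ordinary chi-square test assumes that the two samples compared are independent. Baseline and 6-month findings in one arm come from the same patients, so a test of change within the arm is a paired comparison. The SAP provides for pairing with means and not with categorical variables. An analyst who wants a p-value for change in suppuration within an arm, and who follows the SAP literally, has only chi-square to use. That p-value would be miscalibrated, and with the usual positive correlation between visits it would tend to be too large when nothing has changed. At stake are the within-arm statements on suppuration and hyperplasia, not the randomised comparison.

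**Working it through.** **Inputs.** From the SAP: alpha 0.05, and 45 patients planned. Assumed because the documents do not say: 1:1 allocation (45/2 = 22.5, taken as 22 per arm), two-sided testing, one yes/no value per patient, the prevalence p, and the within-patient correlation φ between two visits. The plan gives no figure for categorical outcomes, so there is none to reproduce. The sample size of 38 rests on bleeding on probing and plays no part here.

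**Step 1: why the level is wrong.** With prevalence p at both visits, the difference between the two observed proportions has variance 2p(1−p)(1−φ)/n. Chi-square uses 2p(1−p)/n. In large samples its true level is therefore P(|Z| > 1.96/√(1−φ)):

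- φ = 0: 1.96, giving 5.0%
- φ = 0.3: 1.96/0.837 = 2.343, giving 1.9%
- φ = 0.5: 1.96/0.707 = 2.772, giving 0.6%
- φ = −0.2: 1.96/1.095 = 1.789, giving 7.4%

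**Step 2: the level at n = 22.** The joint probability of being positive at both visits is p₁₁ = p₁p₂ + φ√[p₁(1−p₁)p₂(1−p₂)]. Summing over all possible paired tables with p = 40% at both visits gives a true level for chi-square of 4.7%, 1.8% and 0.6% at φ = 0, 0.3 and 0.5, and 6.9% at φ = −0.2. Simulation gives 4.6%, 1.8% and 0.6% for the first three. On the same three cases exact McNemar has 2.3%, 1.8% and 1.0%, and mid-P McNemar lies between 2.7% and 4.2%.

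**Step 3: power at n = 22, same enumeration.**

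| Change | φ | Chi-square | Exact McNemar | Mid-P McNemar |
|---|---|---|---|---|
| 60% to 30% | 0.5 | 52% | 65% | 80% |
| 60% to 30% | 0.3 | 52% | 51% | 63% |
| 60% to 30% | 0 | 52% | 38% | 48% |
| 20% to 5% | 0.3 | 29% | 11% | 23% |

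Simulation of the first row gives 51%, 65% and 79%. That row lies near an extreme: p₁₁ cannot exceed 0.30, so φ cannot exceed (0.30 − 0.18)/0.2245 = 0.53.

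**Step 4: one data set.** Take 22 patients with 12 positive at baseline. Six clear and none are new, so 6 remain positive.

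- Chi-square: 44(12×16 − 6×10)²/(22×22×18×26) = 3.385, p = 0.066
- Exact McNemar, 6 against 0 discordant pairs: 2×(1/64) = 0.031
- Mid-P McNemar: 0.031 − 1/64 = 0.016

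With one new case, 7 are positive at the end and the discordant pairs are 6 against 1.

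- Chi-square: 44(12×15 − 7×10)²/(22×22×19×25) = 2.316, p = 0.128
- Exact McNemar: 2×(1+7)/128 = 0.125
- Mid-P McNemar: 0.125 − 7/128 = 0.070

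The choice of test can change the conclusion at 0.05, but one patient is enough to remove the difference.

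**The case against.** The strongest reply is that the misuse is not planned. The phrase "To compare inter and intra group differences" opens the sentence on t-tests and ANOVA. The categorical sentence is separate and mentions neither within-group comparison nor change from baseline. Reading it as a between-group test at a visit is fully consistent with the text, and at patient level that test is not affected by the pairing. This stands, and it makes the point conditional. A reader might infer that the SAP commits the trial to wrong p-values for suppuration and hyperplasia. It does not say so. What remains is that a listed outcome has no stated valid method for change within an arm.

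A second reply is that the harm depends on the inputs. This also stands. A reader might infer that chi-square always hides real improvement. Step 3 shows the reverse at φ = 0 and at low prevalence, and the documents give neither prevalence nor correlation.

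Third, the consequence is small. The trial compares two treatments, its sample size rests on bleeding on probing, suppuration is one of seven listed outcomes, and hyperplasia is not listed. With positive correlation the error is conservative, so no excess of false claims of benefit follows from the pairing. All of this stands.

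Finally, naming McNemar is not enough by itself. Suppuration is scored at 6 sites per implant. If sites were pooled, clustering could push p-values the other way, and McNemar on sites would not cure that. The unit of analysis has to be fixed at the same time.

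**Conclusion.** The point holds in conditional form. If chi-square is used for change within an arm, its p-value is not valid at the nominal level, because that level is right only when the within-patient correlation is near zero. Under the assumptions above, nominal 5% becomes about 1.8% at correlation 0.3 and 0.6% at 0.5. It exceeds 5% only if the correlation is negative, which would be unusual for findings that tend to persist. The effect on power ranges from a loss of 28 points against mid-P McNemar (52% against 80%) to a gain of 6 (29% against 23%), so the case for a paired test rests on validity and not on a promised gain in power.

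A reader might go further and infer that the randomised comparison is compromised. The documents do not support that: a per-patient chi-square between arms at one visit uses different patients in each sample. This is a minor correction to a secondary analysis.

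**What to change.** Replace the categorical sentence in the SAP with:

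> Categorical outcomes are analysed per patient (suppuration positive if present at one or more sites of a treated implant). Between-group comparisons at a visit use the chi-square test. Within-group change from baseline to 6 months uses the McNemar test (mid-P); other visits are descriptive.

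If the sponsor wants all visits tested together, or an analysis by site, the SAP should instead name a method that allows for repeated and clustered observations, such as a GEE or a mixed logistic model. If no within-group test of categorical data is intended, one sentence saying so is enough.

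The cost is SAP wording and, for mid-P, a small calculation from the two discordant counts: with k the smaller count and X binomial on their sum with probability ½, p = 2P(X ≤ k) − P(X = k) when the counts differ. No extra data or patients are needed. The change should be made before the data set is locked.

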- 4. Local Plaque Score. Presence of dental plaque along the mucosal margin at 6 sites of each treated implant recorded after use of disclosing dye and expressed as a percentage of implant sites within each patient.
- 5. Probing pocket depths (PPD) at the implant (6 sites/implant). Recorded at 6 sites of each treated implant to the nearest mm using a plastic probe.
- Recession of the mucosal margin relative to the restoration margin (REC) at the implant buccally. Position of the mucosal margin apical to the restoration margin is positive recession (+), position of the mucosal margin coronal to the restoration margin is negative recession (-).
- Bleeding on probing (BOP) graded 0-3 at the implant (6 sites/implant). Bleeding appearing after measurement of probing depth and expressed as: 0=no bleeding, 1=a dot of bleeding, 2=a line of bleeding, 3=a drop of bleeding
- 8. Presence /absence suppuration (SUP) at the implant (6 sites/implant).
- 9. Presence/absence of bleeding on probing (BOP) at all teeth/implants (4 sites)
- 10. Treatment times
- 11. Patient evaluation of the treatment: Visual analog scale for pain during treatment, the same day after treatment, one day after treatment and three days after treatment. Visual analog scale for aesthetic/satisfaction before the baseline examination and before the examination at 6 months. Postoperativ complications

is asked for in the examination protocol as an open question. Oral health impact profile is measured with the OHIP-14 version.

- All probing measurements will be made using a manual plastic probe.
- Clinical indices concerning probing pocket depths (PPD), bleeding on probing (BOP), plaque and suppuration will be recorded as 6 sites per implant: mesiobuccal, mid-buccal, disto-buccal, disto-lingual, mid-lingual, mesio-lingual.
- Full mouth plaque scores (FMPS) will be recorded as the percentage of total surfaces (4 aspects per tooth/implant) that revealed the presence of plaque (O'Leary et al. 1972). Full mouth bleeding scores (FMBS) will be recorded as the percentage of total surfaces (4 aspects per tooth/implant) that revealed the presence of bleeding.

Statistical power analysis

If BOP is reduced to 30 % \pm 10 in Group A and with 30 % decrease in group B is to be detected at α = 0.05 and a power of β = 0.2, the appropriate number of subjects would be around n = 38. Hence, it is foreseen to incorporate 45 subjects in the study if some of the individuals will not fulfil the study.

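### Missed visits are simply missing and only single-visit tests are planned, so a patient without a 6-month value drops out of the 6-month comparison although BOP and PPD are scheduled at 1 and 3 months

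*SAP*

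**What the plan says.** The SAP's closing sentence is the whole of its missing-data plan: "Non visits will be recorded as missing data in the statistics". For continuous outcomes it states: "To compare inter and intra group differences independent t-test (equal variance not assumed), paired t-test and one-way ANOVA test will be used". For the rest: "For categorical variables non-parametric chi-square test will be used". Neither document defines an analysis set, an imputation rule, a longitudinal model or a sensitivity analysis.

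The Protocol's aim is "To assess the clinical outcome over 6 months following treatment with non-surgical debridement", and its outcome list treats 6 months as the study endpoint. PPD and graded BOP are also due earlier. The list headed "Clinical registrations - 1 month" contains "BOP (6 sites/implant) graded" as well as PPD, and the 3-month list contains both again. Neither list is limited to one arm.

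Some loss is expected. The Statistical power analysis section arrives at about 38 subjects and then says "it is foreseen to incorporate 45 subjects in the study if some of the individuals will not fulfil the study". No dropout rate is given.

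**The concern.** An independent t-test, a paired t-test or a one-way ANOVA at 6 months can use only patients who have a 6-month value. Suppose a patient attends at baseline, 1 and 3 months, is still bleeding, and then stops coming. That patient adds nothing to the 6-month comparison, although two post-treatment measurements are on file.

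Three things are at stake:

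- **Waste.** Collected data that predict the 6-month value go unused.
- **Within-arm results.** If those who leave are the poorer responders, the change from baseline among those who remain is too favourable. The SAP plans within-group tests, so this affects a planned result directly. If such tests are run at several visits (the SAP names none), each may also rest on a different set of patients.
- **Between-arm contrast.** If response-related loss differs by arm, the arm that loses more poor responders looks better than it is. This can happen even when patients in both arms leave at the same level of response, because a true treatment effect puts more patients of the worse arm below that level.

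**Working it through.** **Inputs from the documents.** 45 enrolled and a minimum of 38 (both documents). BOP reduction ±10 points (SAP), read here as an SD. Alpha 0.05, taken as two-sided. Beta 0.2, taken as 80% power.

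**Assumptions not in the documents.** 1:1 allocation (arms of 23 and 22), all withdrawals after the 3-month visit, the correlation between visits, and the link between response and withdrawal.

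**1. The plan's own figures.** The step from 38 to 45 implies a loss of (45 − 38)/45 = 7/45 = 15.6%, and 38/(1 − 0.156) = 45. The 38 itself does not reproduce: the SAP prints the same 30% ± 10 for both arms, a difference of zero, for which no finite sample size exists. That is a separate problem. As a yardstick, 19 completers per arm can detect 10 × (1.960 + 0.842) × √(2/19) = 9.1 points by the normal approximation, or 9.3 points with the t distribution.

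**2. Bias under a graded withdrawal pattern.** Let x be the standardised 3-month BOP. Withdrawal probability is p(x) = 1/(1 + exp(−(a + b·x))), with a set so that the mean of p equals the arm's loss. The shift in the mean 6-month BOP of those who stay is SD × ρ × E[x | stays]. With SD 10, ρ = 0.6 and b = 1.5:

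| Split of 7 losses | Arm of 23: loss, shift | Arm of 22: loss, shift | Between-arm bias | Same, b = 0.5 |
|---|---|---|---|---|
| 4/3 | 17.4%, −1.20 | 13.6%, −0.96 | 0.2 | 0.1 |
| 5/2 | 21.7%, −1.46 | 9.1%, −0.67 | 0.8 | 0.4 |
| 6/1 | 26.1%, −1.73 | 4.5%, −0.36 | 1.4 | 0.6 |
| 7/0 | 30.4%, −1.99 | 0%, 0 | 2.0 | 0.9 |

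With equal loss of 15.6% in each arm, each arm's mean is too favourable by 1.1 points. With no true difference, the shifts cancel in the contrast.

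**3. How likely is 7/0?** If all patients are equally likely to leave, the chance that all 7 come from one arm is [C(23,7) + C(22,7)]/C(45,7) = (245,157 + 170,544)/45,379,620 = 0.9%.

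**4. A sharper pattern.** Here the patients with the smallest 3-month reduction leave, 15.6% overall, with SD 10 and correlation 0.3 / 0.5 / 0.7:

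- No true difference, same threshold in both arms: within-arm reduction overstated by 0.8 / 1.4 / 2.0 points; between-arm bias about 0.
- No true difference, all loss in one arm: spurious difference of 1.5 / 2.5 / 3.6 points.
- True difference 9.1 points, one common threshold (about 6% against 25% leave): estimated difference 8.2 / 7.6 / 6.9 points.

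In this pattern, an estimate that uses the 1- and 3-month values returns the true difference to within about 0.1 point. That is true by construction, because withdrawal was generated from the observed 3-month value.

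**The case against.** The strongest reply has four parts.

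- **The SAP's sentence says how a missed visit is recorded, not how it is analysed.** This is right: case exclusion is an inference. But the named tests offer no other route, and neither document supplies one.
- **The bias in the treatment contrast is small or absent in likely cases.** This largely stands. A reader might infer that the comparison is biased whenever poor responders leave. It is not: with equal loss and no true difference the shifts cancel, and the 2.0-point figure needs a split with about a 0.9% chance under equal risk. What remains is the within-arm bias, the contrast under unequal loss, and the shrinkage when a true effect exists.
- **There is no evidence that loss will follow response or differ by arm.** This also stands. The Protocol's background suggests the laser may cause less discomfort, and a reader might infer from this that loss will differ by device. The documents do not show that discomfort leads to withdrawal, or that it predicts BOP. Scheduled re-treatment and care as needed give patients reasons to stay. Differential loss is a possibility to guard against, not a prediction.
- **A longitudinal model is no cure.** A reader might infer that the 1- and 3-month data would remove most of the bias. The simulations cannot show that, since recovery was built into them. Patients lost before the 1-month visit have no post-baseline value and are outside the model too. Even so, the model uses more of the data under a weaker assumption than case exclusion.

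**Conclusion.** The point holds as a worthwhile and cheap improvement, not as a demonstrated bias in the trial's result. As written, the plan would drop a patient without a 6-month value from the 6-month comparison and ignore that patient's 1- and 3-month measurements.

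Under the assumed graded pattern, the between-arm effect runs from about 0.2 points for near-equal losses to 2.0 points in the extreme case (0.1 to 0.9 with the weaker slope), against about 9.3 points detectable. The figures are illustrative. The documents give neither the correlation between visits nor the withdrawal pattern, and the 7 losses are derived from the two sample sizes, not stated as a planned rate.

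**What to change.** Amend the SAP before the data set is locked and the treatment code broken:

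1. Define a patient-level BOP summary, for example the percentage of implant sites that bleed. The Protocol grades BOP at six sites per implant but gives no patient-level summary of those grades. Use mean PPD per patient alongside it.
2. For the 6-month between-arm comparison of each, fit a repeated-measures linear mixed model to the 1-, 3- and 6-month values, with arm, visit, arm-by-visit and baseline. Include every randomised patient with at least one post-baseline value, and take the 6-month contrast from the model. The planned SPSS package can fit it.
3. Keep the complete-case t-test as a supportive analysis.
4. Report withdrawals and their reasons by arm and by visit.
5. Add a sensitivity analysis that departs from missing at random, for example shifting withdrawn patients' 6-month values toward their baseline over a range. Present it as a stress test: it shows how far the conclusion depends on the assumption, not that the assumption holds. Setting every withdrawn patient to baseline and stopping there would be a single fixed imputation that understates variance.

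The cost is SAP wording and some analysis time, with no new visits, patients or measurements. The downside is that the model assumes missing at random given the observed visits and cannot recover patients with no post-baseline visit.
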